#### **6.4. Study Intervention Compliance**

When participants self-administer study intervention at home, compliance with study intervention will be assessed at each visit. Compliance will be assessed by direct questioning during the site visits and documented in the source documents and eCRF. Deviation(s) from the prescribed dosage regimen must be recorded in the eCRF.

Participants will receive instructions on compliance with study treatment when they begin self-administration of study intervention at home. When participants begin self-administration at home, the investigator or designated study personnel will maintain a log of all study intervention dispensed and returned.

When study intervention is self-administered by participants at home, participants will record all study intervention administrations on a diary card.

During the study, the investigator or designated study research personnel will be responsible for providing additional instruction to reeducate any participant who is not compliant with taking the study intervention.

Compliance with the treatment schedule is strongly encouraged. It is understood that treatment may be interrupted for health-related or safety reasons. Therefore, if for any reason a participant cannot receive a dose of study intervention at the scheduled visit, the participant must make every effort to still come in for the scheduled assessments for that visit. The dose should be administered within 2 weeks of that scheduled visit. Study intervention administrations must be at least 14 days apart. The participant should then resume the normal study schedule relative to the baseline visit (Week 0). In the case when a participant does not come into the investigational site for a scheduled visit, the site will follow-up with that participant. Due diligence could include telephone calls, certified letters, and email requests. Measures taken to obtain follow-up information must be documented.

Study-site personnel will keep a log of all study intervention dispensed and will compare the amount of study intervention dispensed with the amount returned.

All post-baseline visits up to and including Week 24 will have a visit window of  $\pm 4$  days counting from Week 0 as Day 1. After Week 24, all visits will have a visit window of  $\pm 7$  days. The Week 168 visit or the final safety visit (12 weeks after the last dose in participants who discontinued study treatment) will have a visit window of  $\pm 14$  days. If a study visit occurs outside this window, the Sponsor should be consulted about how the participant should resume his or her normal dose schedule.

Information regarding study intervention administrations that are administered outside of the scheduled windows or missed will be recorded. Participant charts and worksheets may be reviewed and compared with the data entries on the eCRFs to ensure accuracy.

## **6.5. Dose Modification**

Not applicable

## **6.6. Continued Access to Study Intervention After the End of the Study**

Participants will be instructed that study intervention will not be made available to them after they have completed/discontinued study intervention and that they should return to their primary physician to determine standard of care.

Local regulations on continued access will always take precedence. Plans for continued access stated in this protocol may change if new information on the benefit-risk profile of guselkumab becomes available during the study or program.

## **6.7. Treatment of Overdose**

For this study, any dose of guselkumab greater than the highest dose at a single dosing visit will be considered an overdose. The Sponsor does not recommend specific treatment for an overdose.

In the event of an overdose, the investigator or treating physician should:

- Contact the Medical Monitor immediately.
- Evaluate the participant to determine, in consultation with the Medical Monitor, whether study intervention should be interrupted or whether the dose should be reduced.
- Closely monitor the participant for AE/SAE and laboratory abnormalities.
- Obtain a serum sample for PK analysis if requested by the Medical Monitor (determined on a case-by-case basis).
- Document the quantity of the excess dose as well as the duration of the overdosing in the eCRF.

## **6.8. Concomitant Therapy**

Prestudy therapies administered after the time of informed consent must be recorded at screening.

Concomitant therapies must be recorded throughout the study beginning with start of the first dose of study intervention to after the last dose of study intervention. Concomitant therapies should also be recorded beyond that point only in conjunction with SAEs that meet the criteria outlined in the protocol.

All therapies (prescription or over-the-counter medications, including vaccines, vitamins, herbal supplements; non-pharmacologic therapies such as electrical stimulation, acupuncture, special diets, exercise regimens, or other specific categories of interest) different from the study intervention must be recorded in the eCRF.

Recorded information will include a description of the type of therapy, treatment period, dosage, route of administration and indication. Modification of an effective preexisting therapy should not be made for the explicit purpose of entering a participant into the study.

The Sponsor or designee must be notified in advance (or as soon as possible thereafter) of any instances in which prohibited therapies are administered.

Every effort should be made to keep participants' concomitant medications for PsA stable through Week 24 or as specified in the following sections. The concomitant medication dose may be reduced or temporarily discontinued because of abnormal laboratory values, adverse effects or intolerance, concurrent illness, or the performance of a surgical procedure but the change and reason for the change should be clearly documented in the participant's medical record.

Participants may not be receiving more than two non-biologic DMARDs from baseline (see Exclusion Criterion 8) through Week 48 (with the exception of participants who are eligible for EE at Week 16, who may receive up to 3 non-biologic DMARDs). After Week 48 and through the end of the study, participants may receive up to 3 protocol permitted non-biologic DMARDs. Note: participants cannot be on concomitant MTX and LEF.

Permitted concomitant medications for PsA and the maximum allowed doses during the study as specified in the following sections are summarized in [Table 3](#).

**Table 3: Permitted Concomitant Medications for PsA and the Maximum Allowed Doses During the Study**

Permitted Concomitant Medications for Psoriatic Arthritis (PsA) a	Maximum Allowed Dose
NSAIDs and other analgesics	Maximum marketed dose approved in the country where the study is being conducted
Oral corticosteroids	Equivalent to 10 mg/day of prednisone
Methotrexate (MTX) b	25 mg/week
Sulfasalazine (SSZ)	3 g/day
Hydroxychloroquine (HCQ)	400 mg/day
Leflunomide (LEF)	20 mg/day

a Permitted concomitant medications are not supplied by the Sponsor.

b It is recommended that all participants taking MTX in this study receive at least 5 mg oral folate or 5 mg folic acid weekly. Guidelines for dose adjustment in the event of MTX toxicity are included in the Trial Center File.

Abbreviations: HCQ = Hydroxychloroquine; LEF = Leflunomide; MTX = Methotrexate; PsA = psoriatic arthritis; SSZ = Sulfasalazine

Participants should not initiate any new treatment for PsA through Week 48, except at Week 16 for those participants who have <20% improvement from baseline in both tender and swollen joint counts (EE criteria). Participants who meet EE criteria will be allowed to initiate or increase the dose of one of the permitted concomitant medications up to the maximum allowed dose as specified in [Table 3](#), as selected by the investigator. Titration to a stable dose of the medication should be completed for participants qualifying for EE by the Week 24 visit.

Beginning at Week 48, the treatment options in [Table 3](#) are allowed to be initiated or dose increased up to the maximum allowed dose specified in [Table 3](#) for participants with ongoing PsA

disease activity at the investigator's judgment; the rationale should be clearly documented in the participant's medical record. Note: participants cannot be on concomitant MTX and LEF.

Concomitant medication review will occur at study visits identified in the SoA (Section 1.3).

### 6.8.1. Non-biologic DMARDs

#### 6.8.1.1. Permitted Non-biologic DMARDs

Participants are permitted to enter the study on a stable dose of up to 2 non-biologic DMARDs (limited to MTX, SSZ, HCQ, or LEF) up to the maximum allowed dose specified in [Table 3](#). Only up to 2 of these non-biologic DMARDs are allowed from baseline through Week 48 (with the exception of participants who are eligible for EE at Week 16, who may receive up to 3 non-biologic DMARDs); participants receiving 3 or more non-biologic DMARDs at baseline are excluded from study participation. After Week 48 and through the end of the study, participants may receive up to 3 non-biologic DMARDs.

At any time during the study, the dose of the permitted non-biologic DMARD may be reduced or temporarily discontinued due to abnormal laboratory values, side effects, concurrent illness, or the performance of a surgical procedure.

Refer to [Table 4](#) for protocol requirements of the permitted non-biologic DMARDs.

**Table 4: Protocol Requirements of the Permitted Non-biologic DMARDs**

Permitted Non-biologic DMARDs	Baseline Usage	Prior to Week 0	Week 0 through Week 48	Week 48 through Week 168
Methotrexate (MTX)	Used	Treatment should have started at least 3 months prior to the first administration of study intervention. Methotrexate routes of administration and doses should be stable for at least 4 weeks prior to the first administration of the study intervention.	Stable dose and route of administration (oral, intramuscular, or subcutaneous permitted) required unless early escape (EE) or unacceptable side effects.	Dose changes allowed up to the maximum dose specified in Table 3 or change of the route of administration, at the investigator's discretion.
	Not Used	Discontinued at least 4 weeks prior to the first administration of study intervention.	Not allowed unless EE.	Allowed up to the maximum dose specified in Table 3 at investigator's discretion.

**Table 4: Protocol Requirements of the Permitted Non-biologic DMARDs**

Permitted Non-biologic DMARDs	Baseline Usage	Prior to Week 0	Week 0 through Week 48	Week 48 through Week 168
Sulfasalazine (SSZ) or Hydroxychloroquine (HCQ)	Used	Treatment should have started at least 3 months prior to the first administration of study intervention. Dose should be stable for at least 4 weeks prior to the first administration of the study intervention.	Stable dose required unless EE or unacceptable side effects.	Dose changes allowed up to the maximum dose specified in Table 3 , at the investigator's discretion.
	Not Used	Discontinued at least 4 weeks prior to the first administration of study intervention.	Not allowed unless EE.	Allowed up to the maximum dose specified in Table 3 at investigator's discretion.
Leflunomide (LEF)	Used	Treatment should have started at least 3 months prior to the first administration of study intervention. Dose should be stable for at least 4 weeks prior to the first administration of the study intervention.	Stable dose required unless EE or unacceptable side effects.	Dose changes allowed up to the maximum dose specified in Table 3 at the investigator's discretion.
	Not Used	Discontinued at least 12 weeks prior to the first administration of study intervention.	Not allowed unless EE.	Allowed up to the maximum dose specified in Table 3 at investigator's discretion.

Abbreviations: DMARDs = disease-modifying antirheumatic drugs; EE = early escape;

HCQ = Hydroxychloroquine; LEF = Leflunomide; MTX = Methotrexate; PsA = psoriatic arthritis;  
SSZ = Sulfasalazine

#### **6.8.1.2. Prohibited Non-biologic DMARDs and Apremilast**

All other non-biologic DMARDs (including, but not limited to chloroquine, gold preparations, penicillamine) and apremilast must be discontinued at least 4 weeks prior to the first administration of study intervention and remain prohibited through Week 168.

#### **6.8.1.3. Systemic Immunosuppressive Drugs**

Systemic immunosuppressants (including, but not limited to azathioprine, cyclosporine, 6-thioguanine, mercaptopurine, mycophenolate mofetil, hydroxyurea, or tacrolimus) must be discontinued at least 4 weeks prior to the first administration of study intervention and remain prohibited through Week 168. If any of these systemic immunosuppressants is initiated during the study, study intervention must be permanently discontinued.

Systemic immunosuppressants do not refer to corticosteroids; see Section [6.8.2](#) for restrictions regarding the use of corticosteroids.

## **6.8.2.      Corticosteroids**

### **6.8.2.1.    Oral Corticosteroids**

Participants using oral corticosteroids at baseline for PsA must be on a stable dose equivalent to  $\leq 10$  mg prednisone per day for at least 2 weeks prior to the first administration of study intervention and continue on this dose through Week 24 unless EE at Week 16.

Starting at Week 24, the dose and type of oral corticosteroid may be adjusted, at the discretion of the investigator (up to the maximum dose in [Table 3](#)), for participants with ongoing PsA disease activity.

Otherwise, throughout the study, the dose and type of oral corticosteroid may be changed at the discretion of the investigator only if the participant develops unacceptable side effects.

Participants not using oral corticosteroids at baseline for PsA must have discontinued oral corticosteroids at least 2 weeks prior to the first administration of study intervention and must not receive oral corticosteroids through Week 24 of the study for PsA. An exception is made for participants who qualify for EE at Week 16.

### **6.8.2.2.    Corticosteroids – Intravenous, Intramuscular, or Epidural Administration**

Intravenous, IM, or epidural administration of corticosteroids for the treatment of PsA are not allowed through Week 48.

Long-term ( $>2$  weeks), oral or IV corticosteroid use for indications other than PsA or psoriasis is not allowed through Week 48. Short-term ( $\leq 2$  weeks) oral, IV, IM, or epidural corticosteroid used for indications other than PsA should be limited to situations where, in the opinion of the investigator, there are no adequate alternatives.

### **6.8.2.3.    Corticosteroids – Intra-articular Injection**

Attempts should be made to avoid intra-articular corticosteroid injections for PsA, especially during the first 24 weeks of the study. However, if necessary, participants may receive up to 2 intra-articular, tendon sheath, or bursal corticosteroid injections in no more than 2 affected sites within any 24-week period of the study. In the case of severe tenderness or swelling in a single joint, it is suggested that the participant be evaluated for infection prior to receiving an intra-articular corticosteroid injection.

### **6.8.2.4.    Corticosteroids – Other Routes of Administration**

Inhaled, otic, ophthalmic, intranasal, and other routes of mucosal delivery of corticosteroids for indications other than PsA and/or psoriasis are allowed throughout the course of the study.

### **6.8.3. Nonsteroidal Anti-inflammatory Drugs and Other Analgesics**

For participants receiving NSAIDs, including aspirin and selective cyclooxygenase two inhibitors, or other analgesics for PsA at baseline, treatment with a stable dose of NSAIDs or other analgesics should have been initiated at least 2 weeks prior to the first administration of study intervention and continue through Week 24 unless EE at Week 16. The dose administered should be the usual marketed dose approved in the country where the study is being conducted.

The use of topical analgesics including capsaicin and diclofenac is allowed and should be recorded in the eCRF. For topical and analgesic patches, the dose should be stable through Week 24 and may be changed only if the participant develops unacceptable side effects.

Participants not receiving NSAIDs or other analgesics for PsA at baseline must have discontinued NSAIDs or other analgesics at least 2 weeks prior to the first administration of study intervention and must not receive NSAIDs or other analgesics for PsA through Week 24 of the study. An exception is made for participants who qualify for EE at Week 16.

Starting at Week 24, participants with ongoing PsA disease activity can initiate or increase the dose of NSAIDs or other analgesics based on the investigator's clinical judgment.

At any time during the study, the dose of NSAIDs or other analgesics may be reduced or temporarily discontinued due to abnormal laboratory values, side effects, concurrent illness, or the performance of a surgical procedure.

Use of NSAIDs and other analgesics for indications other than PsA are permitted throughout the study.

### **6.8.4. Biologic Agents, Cytotoxic Drugs, JAK Inhibitors, or Investigational Agents**

The concomitant use of biologic agents, cytotoxic agents, JAK inhibitors, and/or investigational drugs is not allowed, with the exception of limited emergency use for treatment of COVID-19 infection. Biologic agents include, but are not limited to golimumab, anakinra, etanercept, adalimumab, infliximab, ustekinumab, alefacept, efalizumab, rituximab, natalizumab, certolizumab pegol, tildrakizumab, secukinumab, ixekizumab, brodalumab, and respective biosimilars as applicable. Cytotoxic agents include, but are not limited to chlorambucil, cyclophosphamide, nitrogen mustard, and other alkylating agents. JAK inhibitors include, but are not limited to tofacitinib, baricitinib, filgotinib, peficitinib, upadacitinib and decernotinib. If any of these medications are used, study intervention must be permanently discontinued, with the exception of limited emergency use for treatment of COVID-19 infection. Continuation of study intervention in such cases should be after an appropriate wash-out period and in consultation with the Sponsor's medical monitor.

### **6.8.5. Complementary Therapies**

The use of complementary therapies, including ayurvedic medicine, traditional Chinese medications or non-medicinal therapy such as acupuncture for PsA or psoriasis, is not allowed from 2 weeks prior to the first administration of study intervention through Week 48.

### **6.8.6. Topical Therapy and Ultraviolet B Light**

Concurrent use of topical medications/treatments for psoriasis (eg, topical or intralesional corticosteroids, keratolytics (with the exception of salicylic acid shampoos, which are allowed throughout the study), coal tar (with the exception of coal tar shampoos, which are allowed throughout the study), anthralin, vitamin D3 analogues, or topical tacrolimus, and retinoids) are not permitted through Week 24.

Use of salicylic acid- and tar-containing shampoos is not permitted on the morning prior to a study visit; non-medicated shampoos may be used on the day of a study visit.

Low-potency topical corticosteroids may be used on the face and groin only. Low and mid-potency topical or intralesional corticosteroids (Class III-VII) may be used after Week 24 for psoriasis. High and ultra-high potency corticosteroids (Class I and II) are prohibited through Week 48.

Phototherapy including UVB or tanning beds are not permitted during the study through Week 168. Participants should be encouraged to avoid prolonged sun exposure during the study.

#### **6.8.6.1. Systemic Therapy for Psoriasis**

Concurrent use of systemic therapy for psoriasis (eg, psoralen with ultraviolet light A, systemic retinoids, cyclosporine or tacrolimus, with the exception of those in [Table 3](#)) must be discontinued at least 4 weeks prior to the first administration of study intervention and is not permitted through Week 168; if a systemic antipsoriatic treatment (except those in [Table 3](#)) is initiated during the study, study intervention must be permanently discontinued.

### **6.8.7. Vaccinations (Including COVID-19)**

When considering use of locally-approved non-live vaccines (including emergency use-authorized COVID-19 vaccines) in study participants, follow applicable local vaccine labelling, guidelines, and standard of care for participants receiving immune-targeted therapy.

For study participants receiving a locally-approved (including emergency use-authorized) COVID-19 vaccine, in order to help identify acute reactions potentially related to the COVID-19 vaccine, it is recommended where possible that the vaccine and study intervention be administered on different days, separated by as large an interval as is practical within the protocol.

## 7. DISCONTINUATION OF STUDY INTERVENTION AND PARTICIPANT DISCONTINUATION/WITHDRAWAL

### 7.1. Discontinuation of Study Intervention

A participant's study intervention must be discontinued if:

- The participant withdraws consent to receive study intervention.
- The investigator believes that for safety reasons or tolerability reasons (eg, AE) it is in the best interest of the participant to discontinue study intervention.
- The participant becomes pregnant or plans to become pregnant within the study period. Refer to Appendix 5 [Section 10.5].
- A systemic opportunistic infection.
- The participant is unable to adhere to the study visit schedule or comply with protocol requirements.
- The participant is deemed ineligible according to the following TB screening criteria:
  - A diagnosis of active TB is made.
  - A participant has symptoms suggestive of active TB based on follow-up assessment questions and/or physical examination or has had recent close contact with a person with active TB and cannot or will not continue to undergo additional evaluation.
  - A participant undergoing evaluation has a chest radiograph with evidence of current active TB and/or a positive QuantiFERON®-TB test result and/or 2 indeterminate QuantiFERON®-TB test results on repeat testing (refer to Section 8.2.11) (and/or a positive tuberculin skin test result in countries in which the QuantiFERON®-TB test is not approved/registered or the tuberculin skin test is mandated by local health authorities).
  - The frequency of TB testing can be increased depending on local health authority requirements. Note: In Ukraine, while the QuantiFERON-TB® test is not approved/registered, it is acceptable, and an additional tuberculin skin test is not required.
  - A participant receiving treatment for latent TB discontinues this treatment prematurely or is noncompliant with the therapy.
- The participant has a serious adverse reaction that is temporally related to an injection including a hypersensitivity reaction resulting in bronchospasm, wheezing and/or dyspnea that requires ventilatory support OR that results in symptomatic hypotension with a decrease in systolic blood pressure of 30% from a participant's baseline value or systolic blood pressure <90 mm Hg (Sampson 2006). In general, discontinuation of study intervention administration must be considered for participants who develop a severe injection-site reaction.
- The participant has a reaction resulting in myalgia and/or arthralgia with fever and/or rash (suggestive of serum sickness and not representative of signs and symptoms of other recognized clinical syndromes) occurring 1 to 14 days after an injection of study intervention. These may be accompanied by other events including pruritus, facial, hand, or lip edema, dysphagia, urticaria, sore throat, and/or headache.

- The participant has a malignancy including squamous cell skin cancer. Consideration may be given to allowing participants who develop  $\leq 2$  basal cell skin cancers that are adequately treated with no evidence of residual disease to continue to receive study intervention, after consultation with Sponsor medical monitor or designee.
- The participant has severe liver test abnormalities that are not transient and are not explained by other etiologies, as described in Appendix 8 (Section 10.8).
- The Sponsor may elect to terminate the study at any time, and if the Sponsor decides not to continue development for any reason, study medication/drug will no longer be provided to any participants, including those in the LTE.

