skin test in countries in which the QuantiFERON®-TB test is not approved/registered or the tuberculin skin test is mandated by local health authorities, and, if possible, referral to a physician specializing in TB to determine the participant's risk of developing active TB and whether treatment is warranted. Study intervention administration should be interrupted during the investigation. A positive QuantiFERON®-TB test or tuberculin skin test result should be considered detection of latent TB. Participants with a newly identified positive QuantiFERON-TB® test result must undergo an evaluation to rule out active TB and initiate appropriate treatment for latent TB. Appropriate treatment for latent TB is defined according to local country guidelines for immunocompromised patients. If no local country guidelines for immunocompromised patients exist, US guidelines should be followed, or the participant will be excluded from the study. If the QuantiFERON-TB® test result is indeterminate, the test should be repeated. Participants should be encouraged to return for all subsequent scheduled study visits according to the protocol. Participants who discontinue treatment for latent TB prematurely or who are noncompliant with therapy must immediately discontinue further administration of study intervention and be encouraged to return for all subsequent scheduled study visits according to the SoA (Section 1.3).

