5.3.4.2. Estimand

Adjusted Composite Estimand (Primary)

The **primary** analysis for the primary endpoint will be based on the Adjusted Composite Estimand. This estimand is defined by the 5 components:

- **Population:** Participants with active PsA who are biologic naïve
- **Treatment:**
 - Placebo
 - Guselkumab
- **Variable:** ACR20 composite binary response variable at Week 24, where a responder is defined as a participant who achieves ACR20 response at Week 24 and does not experience ICE categories 1 to 3 prior to that time, in the hypothetical situation where Natural Disaster or Major Disruption and associated ICE categories 4 and 5 did not occur.
- **Intercurrent Events:**
 1. Discontinued study intervention injections due to any reason **except** due to Natural Disaster or Major Disruption.
 2. Initiated or increased the dose of non-biologic DMARDs (MTX, SSZ, HCQ, LEF) or oral corticosteroids over baseline for PsA.
 3. Initiated protocol prohibited medications/therapies for PsA.
 4. Discontinued study intervention injections due to Natural Disaster or Major Disruption.
 5. Severe treatment non-compliance due to Natural Disaster or Major Disruption, defined as ≥ 2 doses of study intervention missed due to Natural Disaster or Major Disruption.
- **Population level summary:** difference in proportion of responders (as per definition of **Variable** above) between guselkumab group and placebo group.

*Note that in the context of ICEs and missing data, the following are defined:

1. **Natural Disaster:** site closure, site access restrictions, or lockdowns caused by COVID-19.
2. **Major Disruption:** the disruption involving Ukraine and neighboring countries/territories beginning February 24, 2022

This estimand examines the difference in proportion of participants who achieve ACR20 response after 24 weeks without increasing/initiating select background PsA medications or discontinuing study intervention (for reasons not due to Natural Disaster or Major Disruption) prior to that point and in the hypothetical scenario where the Natural Disaster or Major Disruptions did not occur,

between each guselkumab group individually versus placebo, amongst participants with active PsA who are biologic naïve.

Additional supplementary analyses will be conducted on the primary endpoint using the Treatment Policy Estimand, aiming to achieve a robust treatment effect for regulatory decision making:

Treatment Policy Estimand (*Supplementary*)

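### Protocol Sections 7.1 and 8.2.11.2 do not state the same consequence for study intervention after a positive on-study TB test

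*Protocol*

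**What the plan says.** Protocol Section 7.1 opens its mandatory list with "A participant's study intervention must be discontinued if". Its TB entries include "A participant undergoing evaluation has a chest radiograph with evidence of current active TB and/or a positive" QuantiFERON-TB result, then "and/or 2 indeterminate QuantiFERON®-TB test results on repeat testing (refer to Section 8.2.11", then a positive skin test in countries where that test is used. A separate entry covers participants who stop latent-TB treatment early or do not comply with it.

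Protocol Section 8.2.11.2, on participants who have had close contact with active TB during the study, requires repeat testing and says: "Study intervention administration should be interrupted during the investigation". It continues: "A positive QuantiFERON®-TB test or tuberculin skin test result should be considered detection of latent TB". Participants with a newly positive QuantiFERON "must undergo an evaluation to rule out active TB and initiate appropriate treatment for latent TB". If no local guidance for immunocompromised patients exists, US guidance is followed or the participant is excluded. An indeterminate test is to be repeated. Then: "Participants who discontinue treatment for latent TB prematurely or who are noncompliant with therapy must immediately discontinue further administration of study intervention".

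In the primary estimand (Protocol 9.4.2; SAP 5.3.4.2 and 5.3.4.3), ICE 1 is "Discontinued study intervention injections due to any reason" other than Natural Disaster or Major Disruption. A participant who meets it before Week 24 is an ACR 20 non-responder whatever was observed.

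**The concern.** The TB findings in 7.1 are joined by *and/or*, so a positive test alone is enough to require discontinuation. Section 8.2.11.2 takes the same finding, calls it latent TB and sets out interruption and treatment. It mentions discontinuation only afterwards, for those who do not keep to the treatment. An investigator reading 7.1 ends study intervention; one reading 8.2.11.2 may hold it and later resume.

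The first thing at stake is consistent handling of a safety event across sites. The second is classification in the primary analysis: two identical participants could receive different ACR 20 outcomes depending on which section the site followed.

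**Working it through.** **1. The two sections side by side**

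| On-study finding | Section 7.1 | Section 8.2.11.2 |
|---|---|---|
| Positive QuantiFERON or applicable skin test | Discontinuation mandatory | Interrupt during work-up; regard as latent TB; rule out active TB; start latent-TB treatment; no instruction to discontinue for the result itself |
| Second indeterminate result | Discontinuation mandatory | Repeat an indeterminate test; silent on what follows a second one |
| Latent-TB treatment stopped or not followed | Discontinuation mandatory | Discontinuation mandatory |

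The third row agrees. The second row is a gap. The permission to proceed after two indeterminate results is in 8.2.11.1 and concerns enrolment. The first row is the inconsistency. Section 8.2.11.2 never says that dosing resumes, but two features imply that it may: it separates interruption from discontinuation, and it makes exclusion the alternative to treatment under guidelines.

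**2. Route to the primary endpoint**

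- Discontinued before Week 24 because of a TB finding: ICE 1, non-response.
- Interrupted because of a TB finding: no ICE category applies. ICEs 2 and 3 concern PsA medication. ICEs 4 and 5 require a Natural Disaster or Major Disruption. The observed Week 24 response is used, or non-response if it is missing for other reasons (SAP 5.3.4.3).
- The outcome therefore differs only for a participant who would have been a responder and whose discontinuation falls before Week 24.
- The key secondary radiographic endpoint uses the treatment policy strategy for ICEs 1 to 3 (SAP 5.3.5.1.3), so observed data are kept on either route.

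**3. Size**

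Inputs from Protocol 9.2.1: ACR 20 rates of 60% on guselkumab and 35% on placebo; 250 or 350 guselkumab against 350 placebo; two-sided alpha 0.05.

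The plan's own figure first. The normal approximation with pooled variance under the null is

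z = [Δ − 1.96·√(p̄(1−p̄)(1/n₁+1/n₂))] / √(p₁(1−p₁)/n₁ + p₂(1−p₂)/n₂), with power Φ(z).

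For 35% against 55% with 350 and 250: p̄ = (122.5 + 137.5)/600 = 0.4333; z = (0.20 − 0.0804)/0.0405 = 2.95; power 99.84%. The same case with 350 per arm gives 99.97%, and the other four rows exceed 99.99%. All six agree with the stated >99%.

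The documents give no rate of on-study positive tests, so f, the fraction of an arm set to non-response under the 7.1 reading, is an assumption, shown over 0.5% to 5%. It is applied to responders at the arm's own rate.

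- All arms affected: difference = (0.60 − 0.35)(1 − f).
- Guselkumab only: difference = 0.60(1 − f) − 0.35.

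| f | All arms (points) | Guselkumab only (points) | Lowest power |
|---|---|---|---|
| 0 | 25.0 | 25.0 | >99.9% |
| 0.5% | 24.9 | 24.7 | >99.9% |
| 2% | 24.5 | 23.8 | >99.9% |
| 5% | 23.8 | 22.0 | >99.9% |

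At 2%, a guselkumab arm's own rate falls by 0.02 × 60 = 1.2 points, but the difference falls by only 0.5 points when all arms are affected alike. One reclassified responder moves an arm's rate by 1/250 = 0.40 points or 1/350 = 0.29 points.

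**The case against.** The strongest reply is that the two sections can be followed in sequence. An investigator could interrupt dosing, rule out active TB, start latent-TB treatment and then discontinue under 7.1, breaking no sentence of 8.2.11.2. That section does not say dosing resumes. It encourages return for visits in much the same terms for participants under investigation and for those who must discontinue. Section 7.1 also cross-refers to 8.2.11. This stands to a point: a reader might infer that the two rules cannot both be obeyed, or that 8.2.11.2 limits discontinuation to non-compliers alone, and the text says neither. What remains is that 8.2.11.2 gives no hint that the positive result itself ends treatment, so a site relying on it would reasonably continue a compliant participant.

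A reader might also infer that 7.1 leaves its own non-compliance rule with nobody to cover. It does not: Inclusion Criterion 16.1 and Section 8.2.11.1 admit participants already on latent-TB treatment or starting it before first dose, and the rule covers them.

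It could be said that the 7.1 lead-in, which speaks of TB screening criteria, confines the list to screening. That fails, because the entries beneath it concern follow-up questions, recent contact and a new diagnosis of active TB, all as reasons to stop treatment.

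Finally, few participants are likely to be affected. The Schedule of Activities places QuantiFERON testing at screening only; later testing follows close contact or local authority requirements. This stands.

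**Conclusion.** The inconsistency is real for a positive on-study test and should be corrected for the sake of clear safety instructions. It rests on an implication in 8.2.11.2 that compliant participants may continue, not on an express statement. The second-indeterminate case is a gap that 7.1 fills; the documents do not support calling it a conflict.

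The documents also do not support reading this as a threat to the primary result. The effect is confined to would-be responders discontinued before Week 24. Over an assumed 0.5% to 5% of participants, the planned difference stays between 22.0 and 24.9 points and power above 99.9%. Those figures depend on the assumed rate and on the planning response rates. The statistical consequence is possible inconsistent classification of individual participants, with a negligible expected effect at trial level.

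**What to change.** Reconcile Protocol Sections 7.1 and 8.2.11.2 so that both state the same consequence for study intervention after a positive on-study QuantiFERON or skin test, including whether dosing may resume after an interruption. Add a cross-reference in 8.2.11.2 that states what follows a second indeterminate on-study result. Which clinical rule applies is for the sponsor to decide.

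The cost is a protocol clarification. The estimand, the ICE definitions and the analysis methods need no change: once the text is settled, ICE 1 as written will classify these participants consistently.
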